#### **Secondary Outcome Measures**

- **Reach: Encounters affected** % clinic encounters where CV Wizard suggests running the full risk assessment tool, i.e., identified a target patient.
- Effectiveness (impact): Patient outcomes 10-year pooled ASCVD risk score change in ASCVD risk score from baseline to last visit of study period (American College of Cardiology-ACC/ American Heart Association - AHA) 10-year pooled ASCVD risk score, 40-75 year olds
- Effectiveness (impact): Patient outcomes last BP ≤140/90 Control of individual CVD risk factors: last BP ≤140/90
- Effectiveness (impact): Patient outcomes last A1c≤8 Control of individual CVD risk factors: last A1c≤8
- Effectiveness (impact): Patient outcomes last LDL<100 Control of individual CVD risk factors: last LDL<100
- Effectiveness (impact): Patient outcomes not current smoker Control of individual CVD risk factors: not current smoker
- Effectiveness (impact): Patient outcomes last BMI ≤25 Control of individual CVD risk factors: last BMI≤25
- Adoption: CDS uptake % of encounters where care team member opts to run the CV
   Wizard risk assessment (explored as both view and print rate and just print rate)
- Implementation: User perceptions Perceived ease of use, usefulness, acceptability of CV Wizard; intent to use it.
- Maintenance over time All measures over 2.5 years of follow-up, Arm 1; 1.5 years, Arm 2.

Table 6. Impact and uptake of the CV Wizard system: Quantitative Measures		
Outcomes, per RE-AIM	Measurement	
Reach:	% clinic encounters where CV Wizard suggests running the full risk assessment tool,	
Encounters affected	i.e., identified a target patient	
Effectiveness (impact):	(i) change in ASCVD risk score (reversible risk; ACC/AHA 10-year pooled ASCVD risk	
Patient outcomes	score, 40-75 year olds; Framingham 30-year CVD risk score, 20-39 year olds).	
	(ii) Control of individual CVD risk factors: last BP ≤140/90; last A1c≤8; last LDL<100;	
	not current smoker; last BMI≤25);	
Adoption: CDS uptake	% of encounters where care team member opts to run the CV Wizard risk	
	assessment	
Implementation: User	Perceived ease of use, usefulness, acceptability of CV Wizard; intent to use it; see	
perceptions	3.3.f.ii	
Maintenance over time	All measures over 2.5 years of follow-up, Arm 1; 1.5 years, Arm 2	
Potential covariates	Measurement	
Patient demographic	Age; gender; race / ethnicity; primary language; poverty level; insurance status at	

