#### **Quantitative Data**

To be included in Aim 1 analyses a patient must have at least one visit in the 6 months after the Arm 1 implementation date at an Arm 1 or Arm 2 CHC and at least one additional visit at a study clinic in the 12-month post-index visit period. The first visit is referred to as the index visit. We will describe those who had inadequate follow-up data (did not have at least one additional visit in the post-index period). For each study subject, CVD risk score / risk factor management status will be calculated at index visit and each encounter during follow-up. While the tool can be run for patients of any age, we will restrict our analyses to patients 40-75 years of age.

We will test for between-group differences in baseline characteristics such as age, sex, race and ethnicity, insurance type, visit count, and health status using chi-square, t-test, and nonparametric Wilcoxon rank-sum tests as appropriate. We will also test for association between baseline characteristics and our outcomes of interest. We will examine the number of patients seen in each service area and clinic and each Arm and compare the characteristics of Arm 1 patients for whom the tool was used to those in Arm 1 for whom the tool was not used and to Arm 2 patients. Because the two arms were selected based on clinic size, percent of patients with a diagnosis for hypertension and the percent of patients that use tobacco, we anticipate there will be differences between the two groups resulting in the need to adjust for these differences. We will also examine characteristics at the service area and clinic-level in Arm 1 for whom the tool was used compared to Arm 1 service areas / clinics for whom the tool was not used and Arm 2 service areas / clinics.

Unadjusted trends in the monthly use and view rates for each of the study CHCs will be explored with use rates defined as: the number of encounters where CV Wizard was printed / number of targeted encounters with high-CVD risk patients per month and view rates defined as the number of encounters where CV Wizard was viewed / number of targeted encounters with high-CV risk patients per month.

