We will also examine overall rates of each of the impact outcomes (BMI in normal range, controlled blood pressure, controlled LDL, controlled HbA1c, and non-smoking status) pre/post tool use to assess any changes in patterns for patients in Arm 1 for whom the tool was used compared to those in Arm 1 for whom the tool was not used as well as to Arm 2 patients. The date the tool was first used for each patient will be assigned as the start of the post-period.

Extent of adoption of a CDS tool like CV Wizard directly impacts its population-level impact. To differentiate between the tool's population level impact versus impact when used, we will conduct intent to treat (ITT) analyses to compare all targeted patients at intervention versus control clinics. We will also conduct effect of treatment on the treated (ETOT; also called per protocol) analyses limited to intervention CHC patients for whom the CV Wizard tool was used (results viewed / printed out) at the index visit, compared to intervention clinic patients for whom it was not used, and separately, to control clinic patients. The ITT analyses test the hypotheses that targeted patients in intervention clinics will have significantly lower CVD risk scores and higher rates of CVD risk factor control, at visits in the year post-index visit period, compared to similar patients in control clinics. The ETOT analyses test the hypotheses that targeted patients in intervention clinics for whom the CV Wizard CDS tool results are viewed and / or printed will have significantly lower CVD risk scores and higher rates of CVD risk factor control, at visits in the year post-index visit period, compared to similar patients in control clinics, and compared to patients in intervention clinics for whom the tool alerted but was ignored at the index visit.

Analyses will be stratified by first-time and repeat patients to see if there is a difference in tool use as well as examine whether the time between visits effects tool use among repeat patients.

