#### **Effect of Treatment on the Treated Analysis**

Per-protocol analyses require adjusting for loss to follow-up and off-protocol therapies or treatments, but if group differences vary too greatly, model misspecification can yield biased estimates. Propensity score methods are an alternative. We will match intervention organization patients in three categories of tool use (never used during follow-up, used once, used more than once) to control organization patients. Counts of tool use will include use at index visit or subsequent study period visits, excluding the last visit. Matching variables will include age, FPL, outcome of interest at baseline, race / ethnicity, sex, count of ambulatory care visits post-index

visit, time from index visit to last study period visit, and clinic rural / urban status. Propensity scores will be estimated using nearest-neighbor matching with replacement.

As analyses in other settings indicated CV Wizard's potential for greater impact among patients with higher baseline risk, analyses of change in reversible risk will be stratified by baseline risk <10% or ≥10%. The assumption being that patients with lower baseline risk are less likely to improve. Additionally, we will run analyses by quartile of baseline reversible risk among patients for whom the tool was ever used during follow-up, matched to controls as described above. Analyses of change in reversible risk will include all patients meeting study inclusion / exclusion criteria; for other outcomes, analyses were restricted to patients with uncontrolled baseline risk. Linear mixed models will be used for all outcomes and checked for normality of residuals.

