#### Statistical Power

To conservatively calculate power for our main outcome (CVD risk score) we estimated 60 clinics with >35 high-CVD risk patients, randomized to two arms; then, using means and standard deviations for this measure from previous studies, we varied effect size associated with the group x time interaction and intraclass correlation. We examined a 1.5%, 2%, 3% greater absolute reduction in risk score over time in intervention vs. control CHCs. Aggressive management can reduce 10-year CVD risk by an absolute 4-5% in high-risk patients in a short time. We do not expect so large an effect and have power to detect smaller effects. **Supplement Addendum (Aim 2b).** This is a 2x2 repeated measures design with two groups of subjects measured at two time points. The primary goal is to compare change across time in group 1 (inperson index encounters) to change across time in group 2 (VC index encounters). A conservative estimate (based on preliminary results from the parent study) of 6000 patients in group 1 and 6000 in group 2 achieve 100% power to detect a difference in mean changes in CVD risk score of 5.0, with a standard deviation of 9.1 at the first time point, a standard deviation of 9.1 at the second time point, and a correlation between measurement pairs of 0.200. The significance level (alpha) is 0.050 using a two-sided, two-sample t-test.

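### The treatment-on-the-treated analyses of BP, A1c and LDL keep only patients uncontrolled at baseline but leave open whether the outcome is yes/no control or the measured value; if yes/no, information is lost and baseline severity goes unmatched

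*Combined protocol and SAP*

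**What the plan says.** Four places in the combined protocol and SAP bear on this.

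- **Entry.** Effect of Treatment on the Treated Analysis (Section 7.a) keeps all eligible patients for reversible risk, but "for other outcomes, analyses were restricted to patients with uncontrolled baseline risk". It does not say which reading, or how many, make a patient uncontrolled. Quantitative Data says that "CVD risk score / risk factor management status will be calculated at index visit and each encounter during follow-up", which points to the index visit.
- **Outcome.** Secondary Outcome Measures (Section 6.a) lists "Control of individual CVD risk factors: last BP ≤140/90" and "Control of individual CVD risk factors: last LDL<100", with A1c at or below 8 in the same form. The treated-analysis hypothesis in Quantitative Data is also about rates: "higher rates of CVD risk factor control, at visits in the year post-index visit period".
- **Model.** The treated section ends: "Linear mixed models will be used for all outcomes and checked for normality of residuals".
- **Matching.** Tool users are matched to control-organization patients. "Matching variables will include age, FPL, outcome of interest at baseline" is how the list of matching variables begins.

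No confirmatory reading, averaging or minimum change is mentioned, and regression to the mean is not discussed.

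**The concern.** If the outcome is control at the cut-off, patients are selected for being on the wrong side of a line and then scored on whether a later value lies on the right side of it. BP, A1c and LDL vary from visit to visit, so some patients cross back with no change in their usual level. Three things would follow.

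- The yes/no indicator discards much of the information in the measured values, in an analysis meant to show what the tool does when it is used.
- A control rate within tool users, all of whom started uncontrolled, would rise without any effect.
- If the matched baseline outcome is also yes/no, it takes a single value in the restricted set and contributes nothing to the match. Tool users and controls could then differ in how far above the cut-off they began, and so in how readily they return below it.

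If the outcome is the measured value, the first problem disappears, but the outcome list and the hypothesis no longer describe what is analysed.

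**Working it through.** **The plan's own figure.** The plan gives no sample size, power or variability for these analyses. Its only numeric power statement is for supplement Aim 2b: 6000 per group, a difference of 5.0 in mean change in risk score, SD 9.1 at both times, correlation 0.200. "The significance level (alpha) is 0.050 using a two-sided, two-sample t-test". SD of change = √(2 × 9.1² × (1 − 0.2)) = 11.51; standard error = 11.51 × √(2/6000) = 0.210; 5.0/0.210 = 23.8 standard errors. The stated 100% power reproduces, but it concerns another outcome and supplies no input here.

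**Assumed inputs (none in the documents).** SBP only. Usual SBP is normal with mean m = 135 or 140 and between-patient SD b = 14 or 18. Each reading adds independent visit noise with SD w = 8, 10 or 12. One index reading above 140 admits; one last reading at or below 140 counts as control. The effect, where there is one, is a 4 mmHg fall.

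**Formulas.**
- SD of a reading: s = √(b² + w²). Correlation of two readings: r = b²/s².
- Last reading given index x: mean m + r(x − m), SD e = s√(1 − r²).
- p0 = average of Φ([140 − m − r(x − m)]/e) over index values above 140. p1 is the same with 144 in place of 140.
- Information kept by the indicator = [(p1 − p0)²/v] ÷ [4²/V]. Here v is the mean of p(1 − p) in the two groups. V is e² for index-adjusted SBP, or the variance of the last reading in the selected patients for unadjusted SBP.

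**One case in full (m 135, b 14, w 10).** s = √(196 + 100) = 17.20; r = 196/296 = 0.662; e = 12.89. Then p0 = 0.334 and p1 = 0.442. v = (0.334 × 0.666 + 0.442 × 0.558)/2 = 0.2345, so the indicator carries 0.108²/0.2345 = 0.0497. Index-adjusted SBP carries 16/12.89² = 0.0963, and the ratio is about 0.52. Unadjusted, V = 205.8, 16/205.8 = 0.0777, and the ratio is about 0.64.

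**Range.** These rows contain the extremes of all twelve combinations, from unrounded values.

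| m / b / w | p0 | p1 | kept vs adjusted | kept vs unadjusted | p0/p1 |
|---|---|---|---|---|---|
| 135/14/10 | 0.334 | 0.442 | 0.52 | 0.64 | 0.76 |
| 135/14/12 | 0.372 | 0.469 | 0.55 | 0.64 | 0.79 |
| 135/18/8 | 0.224 | 0.325 | 0.38 | 0.65 | 0.69 |
| 140/18/8 | 0.185 | 0.276 | 0.34 | 0.63 | 0.67 |
| 140/18/12 | 0.257 | 0.335 | 0.45 | 0.61 | 0.77 |

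Cross-check: when the mean equals the cut-off, p0 = 1/2 − arcsin(r)/π. At 140/18/8, r = 324/388 = 0.835 and p0 = 0.186, which agrees.

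**Sensitivity.** A wider grid (mean 130-145, SD of a reading 15-20, r 0.5-0.9) gives p0 from 11% to 52%. Requiring both systolic and diastolic goals (assumed 135/82, SD 18/11, r 0.5-0.8) gives 37% down to 23%. A1c and LDL would have their own figures.

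**Between-group effect.** Simulating no effect with the same baseline distribution in both groups gave control rates of 27.8% and 27.7%, so the mechanism alone creates no difference.

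**Why baseline severity still matters.** At 135/14/10 with no effect, an index SBP of 142 predicts a last value of 135 + 0.662 × 7 = 139.6, and the chance of reaching goal is Φ(0.03) = 51%. An index of 160 predicts 151.6, and the chance is Φ(−0.90), about 19%. Both patients have the same yes/no baseline status.

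**The case against.** The strongest reply is that the plan may already intend measured values. Linear mixed models with a normality check fit continuous outcomes, and the Intent to Treat Analysis speaks of differences in change. On that reading there is no loss from dichotomizing, and matching would be on the measured baseline. This has force, and it is why the information loss is stated conditionally. It does not settle the matter: the same model is assigned to every outcome, including smoking status, which is yes/no, and Aim 1 defines no measured-value outcome for BP, A1c or LDL.

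Other points against also stand in part.

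- One reading for entry and one for success is an inference. The plan does not define uncontrolled, and its hypothesis refers to visits in the plural, while the outcome list refers to the last value.
- The variability is assumed, the figures are at patient level, and clustering would narrow the gap. With no sample size stated for these analyses, it is not shown that a real effect would be missed.
- Aim 1 names control of individual risk factors as its target, so measured values should not displace it.

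A reader might infer from p0 that a fifth to a third of responders are spurious. That confuses two shares: p0 is a share of index-uncontrolled patients. As a share of observed responders under a 4 mmHg fall, p0/p1 is about 67-79%. A reader might also infer that the comparison is biased in the tool's favour. The documents do not support that: the comparisons are with matched controls or non-users, and the noise falls in both.

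**Conclusion.** The point holds as an inconsistency of scale with a conditional cost. The outcome definition and the hypothesis are yes/no, the specified model is for continuous data, and the entry rule is undefined.

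If the outcome is yes/no, then under the assumed SBP inputs about 19-37% of index-uncontrolled patients reach goal with no effect. The indicator keeps about 34-55% of the information in index-adjusted SBP (61-65% of unadjusted) for a 4 mmHg fall, before clustering.

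The noise is not by itself a between-group bias. The separate weakness is that a yes/no baseline outcome is constant after the restriction and cannot balance severity; the direction of any resulting imbalance is unknown. These are secondary outcomes in a non-randomised comparison. It would be wrong to infer that the Aim 1 primary result is at risk, because the reversible-risk analysis has no such restriction.

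**What to change.** In Effect of Treatment on the Treated Analysis:

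1. State that BP, A1c and LDL are analysed as the last measured value in the linear mixed model, adjusted for the measured index value.
2. State that the matching variable is the measured index value, not control status.
3. Report the declared percentage in control alongside, from a model suited to a binary outcome and adjusted for the measured index value.
4. Define uncontrolled at baseline (which reading or readings, and in what window), and say whether control is judged at the last visit or across visits in the year.
5. Say that control rates within tool users are not to be read as response.

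A sensitivity set needing two out-of-goal readings is optional. At 135/14/10 it lowered the no-effect rate from 0.334 to 0.228 in simulation, but Quantitative Data does not require a reading before the index visit, so first-time patients would tend to drop out.

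The cost is SAP wording and a second set of models on values already extracted. Mean differences are also less familiar to clinics than control rates, which is a further reason to report both.

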## **Secondary Analyses**

Secondary analyses will examine use of the CV Wizard CDSS (main outcome). We will assess which patient-, encounter-, provider-, and clinic-level characteristics are associated with use of the CDS at eligible encounters. Additional analyses will explore the impact of CDS system use on prescribing pattens targeting CVD risk as well as the influence of system prioritization recommendations on risk factor management. We will also analyze results from a provider survey conducted to assess reasons for CV Wizard use and non-use.

Quantitative data will be derived from the CDS data repository and extracted EHR data. Provider survey data was collected from 44 study clinic clinicians conducted midway through the study period.

For quantitative analyses, descriptive statistics will show patient and encounter characteristics included in analyses. After exploring the distribution of the outcome variables to identify the most appropriate model, multilevel models with random effects for provider and clinic will be used to assess (1) multi-level characteristics associated with CV Wizard use and (2) the association between system use and system prioritization on CVD risk factor management.

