characteristics	visit or insurance type through study period; # visits to that site / provider in last	
	year; whether visit was with patient's primary care provider; provider type. Others	
	TBD based on input from clinician advisors.	
Other patient comorbid	Renal function: diagnosed with end stage renal disease or chronic kidney disease;	
conditions	Charlson Comorbidity Score (Modified): Indicator of serious comorbid conditions	
	that may shorten life expectancy, modified to exclude CV components; depression	
	296.xx, 311.xx diagnosis. Other relevant comorbidities TBD.	
Visit type	New patient or established patient	
Provider type	Provider type (PCP or other); # in patient panel	
Other clinic factors	See Table 5; data from baseline survey	
CVD care / process	Measurement	

Recommended care	Whether care suggestions were acted on within 7 days of the encounter; e.g., if CV
that is ordered.	Wizard suggests starting a statin, we will ask whether a prescription was issued.

#### b. Study Aim 2 & 3

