	Note: These outcomes will be adjusted for # of encounters in follow-up	
	period. Analyses of A1c updates will account for whether prior A1c	
	measure indicated lack of control and need for more frequent monitoring.	
	Note: We will consider using coding of a hypertension diagnosis at index	
	and follow-up encounters as a proxy for updated BP.	
Effectiveness (all	Needed care provided within 7 days of encounter, by encounter type; e.g.,	
eligible patients)	If CV Wizard suggested (or would have suggested, if used) starting a statin,	

	was prescription issued: YN; If an A1c test, was the test ordered: YN; If a
	referral to a nutritionist, was the referral made: YN; If medications to help
	quit smoking, was prescription issued; etc.
Effectiveness (subset	Change in CVD risk over time, measured as:
of patients with an	(i) Decrease in total reversible CVD risk score (ACC/AHA 10-year pooled
index encounter and	ASCVD risk score  )
≥1 encounters ≥6 months post-index)	(ii) Change from BP at index visit to increased, decreased, or no change, by end of follow-up period.
,	(iii) Among patients with uncontrolled A1c (>8%) at index encounter, % in
	control by end of follow-up period; among patients with controlled A1c
	(≤8%) at index, % who had a 'relapse' by end of follow-up.
Potential covariates	Description
Patient	Age; gender; race / ethnicity; poverty; insurance status at index; #
characteristics	encounters to site / provider, prior year
Comorbid conditions	Severe mental illness or diabetes diagnosis at index visit
Index characteristics	New patient to the clinic: YN
	l l
Post-index	# in-person / VC encounters between index visit and end of follow-up
Post-index encounters	

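### Prescribing is to be examined by tool use, which is the care team's choice, and no comparison of ordered care by randomised arm is specified

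*Combined protocol and SAP*

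**What the plan says.** All references are to the combined protocol and SAP.

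- **Section 7.a, Secondary Analyses.** "Additional analyses will explore the impact of CDS system use on prescribing pattens targeting CVD risk". The models have random effects for provider and clinic, and one of their targets is "the association between system use and system prioritization on CVD risk factor management". For prescribing, the plan states no arm term, comparator or adjustment set.
- **Use is discretionary.** Section 6.a, Secondary Outcome Measures, defines adoption as the percentage "of encounters where care team member opts to run the CV" Wizard assessment. Secondary Analyses also plans to study what predicts use: "We will assess which patient-, encounter-, provider-, and clinic-level characteristics are associated with use of the CDS at eligible encounters".
- **Ordered care is a listed measure.** The last row of Table 6 records "Whether care suggestions were acted on within 7 days of the encounter". No comparison is attached to it.
- **The ITT analyses do not name it.** Section 7.a, Quantitative Data: "we will conduct intent to treat (ITT) analyses to compare all targeted patients at intervention versus control clinics". The hypotheses follow: "The ITT analyses test the hypotheses that targeted patients in intervention clinics will have significantly lower CVD risk scores", and better risk-factor control. Prescribing and ordered care are not mentioned.
- **The supplement defines need without requiring use.** Its outcome table in Section 6.b counts needed care this way: "If CV Wizard suggested (or would have suggested, if used) starting a statin". Its analyses of that outcome are by encounter type and by use versus non-use, not by arm.

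**The concern.** An order is the step in the causal chain that lies nearest to the tool. If the ITT result on risk is null, the first question is whether care changed at all, and order rates by arm address that directly.

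The analysis as written takes use as the exposure and calls the result an impact. A clinician who has already decided to start or change treatment has a reason to open the tool, and a clinician dealing with an unrelated complaint has a reason to ignore it. Orders would then be more frequent where the tool was used even if the tool changed nothing. The covariates in Table 6 do not record intention, so adjustment for them and random effects for provider and clinic can remove only part of this. The trial could report a selection effect as an effect of the tool, although its own randomisation offers a contrast free of selection by choice of use.

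**Working it through.** The plan gives no figure for prescribing or ordered care, so there is nothing to reproduce. The arithmetic below is illustrative, and its rates, use probabilities and ICCs are assumptions.

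**1. Selection with no tool effect.** Let a share h of encounters be CVD-focused, with order rate r1 in those and r0 in the rest. Let the tool be used in a share a of the CVD-focused encounters and b of the rest. No adjustment is made.

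- Overall use: u = h·a + (1 − h)·b
- Order rate with use: [h·a·r1 + (1 − h)·b·r0] / u
- Order rate without use: [h·(1 − a)·r1 + (1 − h)·(1 − b)·r0] / (1 − u)
- Order rate in either arm: h·r1 + (1 − h)·r0

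With h = 0.30, r1 = 0.40 and r0 = 0.10, each arm has 0.12 + 0.07 = 19.0%, so the arm difference is 0 in every row.

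| a / b | Overall use | With use | Without use | False gap |
|---|---|---|---|---|
| 20% / 20% | 20.0% | 19.0% | 19.0% | 0 |
| 30% / 15% | 19.5% | 0.0465/0.195 = 23.8% | 0.1435/0.805 = 17.8% | 6.0 points |
| 40% / 10% | 19.0% | 0.055/0.19 = 28.9% | 0.135/0.81 = 16.7% | 12.3 points |
| 60% / 10% | 25.0% | 0.079/0.25 = 31.6% | 0.111/0.75 = 14.8% | 16.8 points |

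**2. Extreme case.** Let intention equal ordering (r1 = 1, r0 = 0), with h = 0.20 and b = 20%.

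- a = 40%: 0.08/0.24 = 33.3% with use, 0.12/0.76 = 15.8% without; gap 17.5 points.
- a = 60%: 0.12/0.28 = 42.9% with use, 0.08/0.72 = 11.1% without; gap 31.7 points.

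**3. Is the arm comparison available?** Index visits fall in the 6 months after Arm 1 implementation (Section 7.a, Quantitative Data), and Arm 2 starts 18 months after Arm 1 (Section 4). A 7-day order window therefore closes well before Arm 2 activation. Section 9 extracts data for all target patients at the study clinics. The outcome needs no second visit, so it can be measured on all targeted index encounters.

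**4. Dilution.** If the tool changes orders only where it is used, the arm effect is the use rate times the effect when used. A 10-point effect when used becomes 1, 2, 4 or 8 points at 10%, 20%, 40% or 80% use. Section 6.b names 80% of targeted visits as the desired level.

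**5. Precision of the arm comparison.** Take 30 clinics per arm and 35 patients per clinic (the power section assumes 60 clinics with more than 35 each). The design effect is 1 + 34·ICC and the effective size per arm is 1,050 divided by it. Differences detectable with 80% power at two-sided 0.05:

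| ICC | Design effect | Effective n per arm | Control rate 10% | 20% | 30% |
|---|---|---|---|---|---|
| 0.01 | 1.34 | 784 | 4.6 points | 5.9 | 6.7 |
| 0.05 | 2.70 | 389 | 6.8 | 8.6 | 9.6 |
| 0.10 | 4.40 | 239 | 9.0 | 11.2 | 12.3 |

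More patients per clinic help only up to a limit. At ICC 0.01 and a 20% control rate, the floor is 2.8 × √(2 × 0.16 × 0.01 / 30) = 2.9 points.

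**The case against.** **The plan does not rule out an arm comparison.** A reader might infer that prescribing will be judged only by users against non-users. The text does not go that far. The prescribing analysis is exploratory and names no comparator, the treated-patient analyses elsewhere also compare users with control-clinic patients, and the ITT model paragraph covers outcomes other than reversible risk without listing them. What stands is that no arm comparison of ordered care is specified. If Arm 2 patients were the comparator for users, the users would still be self-selected.

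**Scope.** Aim 1 concerns risk scores and risk-factor control. Ordered care is a process row in Table 6, not a primary or bulleted secondary outcome, and what follows use is a legitimate question. This is fair, and the primary inference is untouched. It does not justify calling a by-use association an impact.

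**Size.** A reader might take 17 to 32 points as the expected bias. That range needs every intended encounter, and no other, to end in an order. At the same 2:1 use ratio the milder mechanism gives 6.0 points rather than 17.5. Both ignore adjustment.

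**Dilution.** This objection largely stands. At 20-40% use, a 10-point effect when used gives 2 to 4 points by arm, below every detectable difference in the table above. The arm comparison could well return an uninformative null.

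**Feasibility.** Section 7.a requires risk scores and control status in both arms, not treatment suggestions. The documents describe no silent run of the algorithm in Arm 2 before activation, and the definition of need that does not depend on use belongs to the supplement. The data appear to be there, but the derivation is not shown.

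**Explaining a null.** Use rates, analyses by amount of use, the provider survey and the qualitative work would help, so it is too strong to say that the trial could not interpret a null. None of them measures ordering by arm.

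**Conclusion.** The point holds in a limited form. No comparison of prescribing or ordered care by randomised arm is specified, and the planned prescribing analysis uses an exposure that the care team chooses, so its estimate is open to confounding by intention to act. With no tool effect and no adjustment, the false gap is about 6 to 17 points under the milder assumptions and up to about 32 in an extreme case. These figures show that the bias can be large, not that it will be.

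The arm comparison removes selection by choice of use, but not every selection, because patients still enter through visits made after Arm 1 go-live. It estimates the effect of having the tool available, so it complements the by-use analysis and does not replace it.

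**What to change.** 1. Add an ITT comparison by arm: among targeted patients' index encounters before Arm 2 activation, the proportion of needed care ordered within 7 days. Derive need identically in both arms from EHR data, using the supplement's definition of what the tool suggested or would have suggested. If that cannot be derived for Arm 2, compare CVD-related prescribing by arm instead.
2. Use the ITT clustering structure with a binary-outcome model. A patient random effect is needed only where a patient contributes more than one suggested action.
3. If the ITT model paragraph was already meant to cover ordered care, say so by name.
4. Keep the by-use prescribing analysis, state its comparator and adjustment set, and call it an observational association rather than an impact.
5. Report the arm result beside the use rate at index encounters, and state in advance that a null by arm does not show absence of effect when the tool is used.

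The cost is analysis and programming time, including a derivation of need for Arm 2 that the documents do not yet describe. No new data collection is evident. The scientific cost is the dilution shown above.
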